Main Eligibility Criteria	
Inclusion Criteria
 
 1. Adult patients at least 18 years of age 2. Current diagnosis of cystic fibrosis 
Exclusion Criteria
 
A potential subject who meets any of the following exclusion criteria is ineligible to participate in the study.
 
 1. Inability to commit to at least 3 months of use of the fitness tracker and routine follow up in CF clinic 2-5 months from enrollment. 2. Inability to speak and understand English 3. Those patients without dedicated access to a smartphone, or tablet with internet and blue tooth capabilities. 4. Those unwilling to sign an informed consent form
Study Rationale	Cystic fibrosis is a hereditary condition that for most leads to a significantly shortened lifespan and impaired quality of life. The CF research community has strived for new interventions to improve lung health with dramatic improvements in patient survival over the last 20 years. Fitness trackers could be helpful for those with CF through evaluating general trends in activity level, intensity of activity and sleep quality and timing. Further, integration of data from

	wearable health tracking with objective biologic/medical data would allow analysis of trends between these core components of a healthy lifestyle and medical outcomes. The objective of this pilot study is to demonstrate the feasibility of integrating the personal health tracker data with the medical data stored in CFFPR to facilitate larger multicenter interventional studies to continue improving care in this deserving population
Primary Objectives	To provide proof of concept for integrating existing medical data from CFFPR with long term monitoring of patterns in sleep and activity available through individual fitness trackers (i.e. Fitbit).
Secondary Objectives	AIM 1: Demonstrate that participants will consistently use and upload data from the fitness tracker as measured by use of at least 20 hours per day and uploading of at least 75% of activity. AIM 2: Develop integration tool for the data from the Fitbit with data from CFFPR AIM 3: Analyze the data trends from the Fitbit for activity and sleep with health trends from the CFFPR (FEV1, BMI, exacerbation rates).
Endpoints	Results of the project will allow the CF foundation to determine if integration of these databases is feasible. Ability to develop interventional studies using fitness trackers with interventions with exercise/sleep therapies
Study Design	Single-center pilot, correlational study to provide proof of concept for integrating existing medical data from CFFPR with long term monitoring of patterns in sleep and activity available through individual fitness trackers (i.e. Fitbit).
Study Agent/ Intervention Description	Fitbit tracker; is an activity tracking product that is wireless-enabled wearable technology device that measures data such as the number of steps walked, heart rate, quality of sleep, steps climbed, and other personal metrics involved in fitness
Number of Subjects	21
Duration of Follow up	3-5 Months
Estimated Time to Complete Enrollment:	12 months
Statistical Methodology:	For Aim 1 and Aim 2 we will report descriptive statistics, such as mean, median and standard deviation, for the number of days of use, days of use over 20 hours and average hours of use per day (total hours of use/total days of use) in the study. For Aim 3. We will conduct explorative data analysis to get preliminary information for designing a full-scale prospective study. First, we will report summary statistics, such as mean, median, standard deviation and quartile range, for continuous measurement and percentage for binary measurement, of heart rate, activity levels, sleep time and quality of sleep for every month and summary statistics for FEV1, BMI and CF exacerbation at enrollment and 3-month and differences between enrollment and 3-month. To identify

	what information of heart rate, activity levels, sleep time and quality of sleep is potentially associated with the differences between enrollment and 3-month in FEV1 and BMI and CF exacerbation for 3- month, we will use Pearson correlations for FEV1 and BMI and comparing means or medians of the wearable metrics between the subgroups with and without CF exacerbation in 3 months. We will also consider mean or median values of the wearable metrics measured last 3-2-1-month prior to the follow-up to determine the extent to how latest metrics are associated with clinical outcomes.
Efficacy Assessments	To measure the benefit of using Fitbit trackers for those with CF through evaluating general trends in activity level, intensity of activity and sleep quality and timing (Jankelowitz et al., 2005). Further, integration of data from wearable health tracking with objective biologic/medical data would allow analysis of trends between these core components of a healthy lifestyle and medical outcomes.
Unique Aspects of this Study	This pilot study is to demonstrate the feasibility of integrating the personal health tracker data with the medical data stored in CFFPR to facilitate larger multicenter interventional studies to continue improving care in this deserving population

STUDY CALENDAR

The below study chart is described in detail in Section 5 Study Procedures.

Period/ Procedure	Screening/Enrollment	2-5 monthFollow up visit		Sick Visit
		1	2	
Study Day/Visit Day				
Eligibility Criteria	X			
Informed Consent	X			
Demographics	X			
Assessment of Adverse Events			X	X
Device Administration				
Fitbit Inspire HR provided	X			
Fitbit Training	X			
Sync Device every 5 days	X		X	X
Questionnaires				
CF QOP	X		X	X
PQSI	X		X	X
Medical history collected as standard of care				
Lung Function	X		X	X
BMI	X		X	X

Period/ Procedure	Screening/Enrollment	2-5	Sick Visit
		month	Follow up visit
Study Day/Visit Day	1	2	3
CF exacerbation rate	X	X	X

TABLE OF CONTENTS

PROTOCOL SIGNATURE PAGE	2
REVISION HISTORY	4
PROTOCOL SUMMARY	5
INCLUSION CRITERIA.....	5
EXCLUSION CRITERIA.....	5
FITBIT TRACKER.....	6
STUDY CALENDAR	7
LIST OF ABBREVIATIONS	11
1 BACKGROUND	12
CYSTIC FIBROSIS.....	12
2 HYPOTHESIS AND OBJECTIVES	14
2.1 AIMS	15
AIM 1:	15
AIM 2:	15
AIM 3:	15
3 STUDY DESIGN.....	15
3.1 GENERAL DESCRIPTION	15
3.2 STUDY TIMELINE	16
SEE STUDY CALENDAR.	16
4 PATIENT SELECTION.....	16
4.1 ELIGIBILITY CRITERIA	16
4.2 INCLUSION CRITERIA	16
4.3 EXCLUSION CRITERIA	16
5 STUDY ENTRY AND WITHDRAWAL; STUDY PROCEDURES	16
5.1 STUDY ENTRY PROCEDURES	16
5.2 STUDY WITHDRAWAL PROCEDURES	17
6 TREATMENT PLAN.....	17
6.1 STANDARD OF CARE PROCEDURES	17
6.2 FOLLOW-UP PERIOD	18
7 ADVERSE EVENTS: DEFINITIONS AND REPORTING REQUIREMENTS	19
7.1 DEFINITIONS	19
7.2 MOST MONITORING AND RECORDING AN ADVERSE EVENT	21
8 PHARMACEUTICAL INFORMATION	23
9 STATISTICAL CONSIDERATIONS	23
9.1 STUDY DESIGN	23
9.2 SAMPLE SIZE AND POWER ESTIMATE	23
9.3 REPLACEMENT POLICY	23

9.4 INTERIM ANALYSES AND STOPPING RULES	23
9.5 ANALYSES PLANS	23
9.6 STUDY TEAM	23
9.7 QUALITY ASSURANCE.....	23

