certain areas of brain (specifically the retina and anterior hypothalamus) could contribute to both changes in the timing of sleep and the quality of sleep (Jensen et al., 2017). The role of sleep alterations in glucose metabolism has been studied (Gonzalez-Ortiz, Martinez-Abundis, Balcazar-Munoz, & Pascoe-Gonzalez, 2000; Punjabi et al., 2002), but no clinical study of CF Related Diabetes and sleep patterns or exercise patterns has been completed (Hardin, Leblanc, Marshall, & Seilheimer, 2001).

The newest personal fitness monitors allow for both short term and long-term trending in activity and sleep and are both affordable and easy to operate. Data generated by this technology afford the possibility of better understanding one's personal state of general wellness from how much activity to the level of intensity to the quality and quantity of sleep one is getting. The role of an activity monitor in improving activity and fitness has been studied and may have the most impact

on those with lowest activity levels in some populations (Beattie et al., 2017; Schrager et al., 2017). Regarding sleep tracking, the validity of sleep tracking programs has also been assessed and total sleep time and sleep quality can be measured with fair accuracy (de Zambotti, Baker, & Colrain, 2015; Meltzer, Hiruma, Avis, Montgomery-Downs, & Valentin, 2015).

Fitness trackers could be helpful for those with CF through evaluating general trends in activity level, intensity of activity and sleep quality and timing (Jankelowitz et al., 2005). Further, integration of data from wearable health tracking with objective biologic/medical data would allow analysis of trends between these core components of a healthy lifestyle and medical outcomes.

The CF community has been collecting biologic/medical data on patients now for over 30 years through the CF Foundation Patient Registry (CFFPR). This provides individual as well as center specific trends through tracking weight/BMI, lung function, frequency of exacerbations as well lab and test results such as glycemic control and bone density results. This data has assisted CF centers in improvements in care delivery (Warwick, 2001) through quality improvement (Johnson,

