Butler, Konstan, Morgan, & Wohl, 2003) and best practice sharing between centers (Schechter, Fink, Homa, & Goss, 2014). In 2017 all centers have now risen to near real-time reporting of lung function, exacerbation rates, weight and diabetes control trends for patients to encourage conversations and real behavior change around medical adherence.

The objective of this pilot study is to demonstrate the feasibility of integrating the personal health tracker data with the medical data stored in CFFPR to facilitate larger multicenter interventional studies to continue improving care in this deserving population.

Methods

Potential subjects will be identified during regular team meetings held by a dedicated care team for CF patients that includes members of the study staff. Patients who are identified as potential participants will be contacted by a trained member of the study team to discuss participation. The study team will work with patients to arrange for signing of an informed consent form at their next scheduled clinic appointment.

All subjects will be consented to participate in this observational study for a minimum 3 months to accommodate their clinic schedule. There will be a minimum of 2 clinical visits after enrollment (clinical visit 1 at set up and 2-5 months follow up) as well as any sick visits. This visit schedule was selected to coincide with current care schedules.

At the initial visit all consented subjects will be provided a Fitbit Inspire HR and shown the proper use and care of the tracker. The research coordinator will confirm the subject's ability to upload data from the device to their study Fitbit account (deidentified) under direct observation. The subjects will also receive instruction in how to document their activity and sleep in the diary app associated with their Fitbit. (The subjects will have access to instructional videos and help desk

through the Fitbit resource center as well). The research coordinator will monitor the study specific FitaBase for the duration of the study (once a week for 3 months) and contact the patient via their preferred method of contact with encouragement to consistently upload data if needed.

During the initial visit and any follow up clinic visits subjects will complete a general quality of life in CF survey-CF QOL and a sleep quality index-Pittsburgh Sleep Quality Index (PQSI) through Redcap to assist in a comprehensive integration of data.

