3 STUDY DESIGN

3.1 General Description

The study center has identified 147 adult patients ranging from 18 to 69 years of age with CF. For this feasibility study a total of 21 patients will be enrolled and while we will not assign patients to cohorts or limit enrollment based on lung function at the end of the study, we will stratify enrolled patients to explore trends. The cohorts will be constructed ad hoc to facilitate an accurate and clinically meaningful analysis. This will allow for trend analysis to see if more advanced disease is a factor in adherence to use of the Fitbit and an exercise regimen.

The study will be carried out by a dedicated research group consisting of seven full time research coordinators, a research assistant, and a part-time systems specialist within the PI's Division that has conducted numerous trials and continues to support a robust and successful CF research program. The study will be assigned at minimum two research coordinators to provide every eligible patient the opportunity to participate. The study research coordinator group has previous experience with fitness tracker software and management of deidentified database related to a fitness tracker used in a large multicenter clinical trial.

Number of Subjects

Up to 21 patients may be consented into this trial. Twenty-one patients are needed to meet the aims of this trial.

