9.11 Institutional Review Board

The protocol, the proposed informed consent form and all forms of participant information related to the study (e.g. advertisements used to recruit participants) will be reviewed and approved by the MCW Institutional Review Board. The initial protocol and all protocol amendments must be approved by the IRB prior to implementation.

Informed Consent Process

Informed consent is a process that is initiated prior to the individual's agreeing to participate in the study and continues throughout the individual's study participation. Extensive discussion of risks and possible benefits of this therapy will be provided to the subjects and their families. Consent forms describing in detail the study interventions/products, study procedures, and risks are given to the subject and written documentation of informed consent is required prior to starting intervention/administering study product.

Potential subjects will be told, and a statement will be included that this study is designed to determine both safety and effectiveness. The consent forms will include the approved MCW IRB template language.

Consent forms will be IRB-approved and the subject (and Legally Authorized Representative, if necessary) will be asked to review the document. Upon reviewing the document, the investigator will explain the research study to the subject and answer any questions that may arise. In accordance with 46 CR 46.111, the subject will sign and date the informed consent document prior to any procedures being done specifically for the study.

A witness should only sign when required, per FH/MCW IRB policy. If a witness signs the document when not required, the study staff should document in the legal medical record (or note to file) the relationship to the patient and why a witness signed. (i.e., "Although not required, the subject's spouse was present during the consenting process and signed as the witness." Or "Although not required, hospital staff was present for consenting process and signed as a witness.")

The subjects (or their LAR) will have the opportunity to discuss the study with their surrogates or think about it prior to agreeing to participate. The subjects may withdraw consent at any time throughout the course of the trial.

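### The Efficacy Assessments row and Section 9.11 promise benefit, safety and effectiveness, which this one-group feasibility study cannot determine

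*Combined protocol and SAP*

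**What the plan says.** Two places state a purpose of showing an effect.

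- **Protocol Summary, Efficacy Assessments.** The row opens "To measure the benefit of using Fitbit trackers for those with CF through evaluating general trends in activity level" and goes on to name intensity of activity and the quality and timing of sleep. Its second sentence concerns trends between these components and medical outcomes.
- **Section 9.11, Informed Consent Process.** Potential subjects are to be told that "this study is designed to determine both safety and effectiveness".

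The rest of the protocol describes a different study.

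- **Protocol Summary, Study Design:** "Single-center pilot, correlational study to provide proof of concept".
- **Section 1, Methods:** "All subjects will be consented to participate in this observational study for a minimum 3 months", and "all consented subjects will be provided a Fitbit Inspire HR" at the initial visit.
- **Section 3.1:** "we will not assign patients to cohorts or limit enrollment based on lung function". Strata are to be formed ad hoc at the end.
- **Section 2.1:** the three aims are tracker use and upload, a tool to integrate Fitbit and registry data, and association of tracker trends with FEV1, BMI and exacerbation.
- **Section 3.1.1:** the analyses are descriptive statistics, Pearson correlations, and a comparison of wearable metrics between subjects with and without an exacerbation.

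**The concern.** To measure the benefit of using a tracker, or to determine its effectiveness, outcomes with the device must be compared with outcomes without it. The plan generates no data of the second kind. If the Efficacy Assessments row is taken at its word, a change in activity or sleep while the tracker is worn could be reported as a benefit of wearing it, and that claim could pass into the interventional studies this pilot is meant to inform.

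The protocol itself shows why on-device data are not a neutral baseline. Section 1 says of monitors: "The role of an activity monitor in improving activity and fitness has been studied and may have the most impact" on the least active people in some populations. A trend within the study could therefore mix a device effect, the novelty of the device and the patient's own course.

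The Section 9.11 sentence matters for a separate reason. It directs what people are told before they agree to take part, and it describes a purpose that the study cannot fulfil.

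**Working it through.** **1. Can a tracker effect be estimated?** Write the mean change in activity over the study as

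observed change = device effect + novelty + natural course and other care.

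The design gives one group, all with the device. Separating the first term from the others needs either a concurrent group without the device or a period without it in the same patients.

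- *Comparator:* none. All consented subjects get the device (Section 1, Methods; Section 5.1.2). Section 5.1.1 says that consented patients are registered and randomized in OnCore, but no arms, allocation ratio or control condition appear anywhere, so that word supplies no comparator.
- *Activity before the device:* none. The Study Calendar provides the Fitbit at Screening/Enrollment and lists no run-in and no earlier activity measure. The same holds for sleep as measured by the tracker.
- *Other enrollment values:* lung function, BMI, exacerbation rate, the quality-of-life survey and the sleep-quality questionnaire are recorded at enrollment. A before-after change in these can be described. Without a comparator it cannot be attributed to the tracker.

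There is one observed quantity and more than one unknown, and enrolling more patients does not change that.

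**2. Do the figures in Section 9.2 bear on a tracker effect?** They were reproduced first.

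- Correlation, n = 21, interval tanh(atanh(r) ± 1.96/√(n − 3)), where 1.96/√18 = 0.462:
  - r = 0.1: −0.347 to 0.510, width 0.856 (plan: 0.856).
  - r = 0.9: 0.766 to 0.959, width 0.193 (plan: 0.193).
- Difference in means, SD = 1, half-width t(0.975, n1 + n2 − 2) × √(1/n1 + 1/n2):
  - 10 and 10: 2.101 × 0.447 = 0.940 (plan: 0.940).
  - 7 and 14: 2.093 × 0.463 = 0.969 (plan: 0.969).

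All four match. They give the precision of a correlation and of a split by exacerbation status. None is a precision for device versus no device.

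**3. Can safety be determined?** The Study Calendar has adverse events assessed at the follow-up and sick visits, and Section 7 defines their grading and reporting. Section 7.1.1 expects no study-related events. Neither Section 3.1.1 nor Section 9 names a safety endpoint or analysis. As an illustration, assume 0 related events in 21 subjects:

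- one-sided 95% upper bound: 1 − 0.05^(1/21) = 13.3%;
- upper limit of a two-sided 95% interval: 1 − 0.025^(1/21) = 16.1%.

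A clean record would thus remain compatible with a related-event rate of about one in eight. That is a description of safety and falls short of determining it.

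**The case against.** The strongest reply is that the operative text already says the right thing. The objectives, aims and analyses are those of a feasibility and association study, Aim 3 is labelled exploratory, and an uncontrolled design suits such aims. This stands. The fault lies in two statements, and the design needs no change.

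Second, the Efficacy Assessments row nearly repeats a sentence in the Study Rationale and Section 1 saying that trackers could be helpful through evaluating trends. Read that way, benefit means usefulness for monitoring. The milder reading is possible, but under a heading of efficacy, and with the opening changed to measuring benefit, it is not what most readers would take from the row.

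Third, Section 9.11 looks like template text. It sits near other drug-trial language, such as the references to study drug administration in Section 7.2 and the IND precondition in Section 9.10. That may explain the sentence, but it remains a directive about what subjects are told.

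Fourth, adverse events can be described in one group, so the absence of a comparator does not defeat safety. This is right. The case on safety rests on the missing endpoint and analysis and on the small number of subjects.

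A reader might also infer that the planned enrollment-to-follow-up differences in FEV1 and BMI are meant as evidence of device benefit. The documents do not support this. The benefit sentence names only activity and sleep, and Section 3.1.1 summarises the clinical differences and then uses them as outcomes in correlations with the wearable metrics. No analysis attributes them to the tracker.

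**Conclusion.** The two statements are wrong as written, because they claim a property that the design lacks. The effect of wearing the tracker on activity or sleep is not estimable: there are no control patients and no activity or tracker-measured sleep data from before the device. Safety can be described in 21 subjects but not determined. The formal aims and the four precision figures are unaffected, and no number in the plan changes.

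Two further inferences would go too far. One is that the study has no pre-device measurements at all; several clinical and questionnaire values are taken at enrollment. The other is that all 21 subjects were given a wrong statement of purpose. The consent form is not among the documents reviewed, so this holds only if the form follows Section 9.11.

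The conclusion rests on the calendar being complete as to activity measurement, and on the word randomized in Section 5.1.1 having no allocation behind it. The 13.3% bound assumes zero related events and is illustrative only.

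**What to change.** 1. **Efficacy Assessments row.** Replace with: *To describe trends in activity, intensity and sleep and their association with FEV1, BMI and exacerbation; no benefit of the tracker will be inferred, because there is no comparator and no pre-device measurement of activity or tracker-measured sleep.*
2. **Section 9.11.** Replace the statement on safety and effectiveness with the feasibility and association purpose given in the Protocol Summary objectives and Section 2.1, and check that the consent form says the same.
3. **Section 3.1.1 (optional).** State that enrollment-to-follow-up differences are descriptive and will not be attributed to tracker use.

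The cost is a wording amendment with IRB approval, as Section 9.14 requires, and a check of the consent form. No patients, visits or data are added. The sponsor gives up only a claim that the design cannot support.
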